8.1.2.3 Statistical Methods

The proportion of Treatment Subjects with Treatment Success through the Day 360 Assessment will be estimated using the Kaplan-Meier method. The 97.5% one-sided lower confidence limit of the observed Treatment Success rate will be compared to the performance goal of 40%. If the lower confidence limit is greater than the performance goal, the null hypothesis will be rejected. The confidence limit will be calculated as the pointwise confidence limit using the log-log methodology.

Each Treatment subject will be classified as Treatment Success (event-free) or Treatment Failure (primary effectiveness endpoint event). Subjects who withdraw or die from the study prior to the Day 360 Assessment, without experiencing a primary effectiveness endpoint event, will be censored on the date of withdrawal or death. Subjects who are determined to be Severe COVID-19 Subjects during trial participation without experiencing a primary endpoint event will be censored as of the Onset Date of the condition.

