6.4 Withdrawal

All subjects enrolled in the clinical study (including those withdrawn from the clinical study) shall be accounted for and documented. If a subject withdraws from the clinical investigation, the reason(s) shall be reported. If such withdrawal is due to problems related to investigational device safety or performance, the Investigator shall ask for the subject's documented permission to follow his / her status / condition outside of the clinical study.

Reasons for withdrawal may include physician discretion, subject choice to withdraw, lost to follow-up, or death. While study withdrawal is discouraged, subjects may withdraw from the study at any time, with or without reason, and without prejudice to further treatment. In the event a subject does decide to withdraw from the study, every effort should be made to obtain full information on any ongoing reportable adverse events up to the point of withdrawal. Additional data may no longer be collected after the point at which a subject has been withdrawn from the study or withdraws his / her consent, for whatever reason. Data collected up to the point of subject withdrawal may be used, unless any local regulations apply which require removal of the data.

If the withdrawal is due to the Investigator's discretion, the Investigator is obligated to follow all open reportable adverse events until they can be considered as resolved or not resolved.

The outcome of all open reportable adverse events should be documented. If the withdrawal is due to problems related to device safety or performance, the Investigator shall ask for the subject's documented permission to follow his / her status / condition.

Withdrawn subjects will not be replaced.

All applicable electronic case report forms (eCRFs) up to the point of subject withdrawal / lost to follow up and an "End of Study" eCRF must be completed.

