6.5 Lost to Follow-Up

A subject will be considered lost to follow-up if he or she fails to return after documented attempts to attend a scheduled assessment and is unable to be contacted by the study site staff.

The following actions must be taken if a subject fails to participate in a required study assessment:

- The site will attempt to contact the subject to reschedule the missed assessment and counsel the subject on the importance of maintaining the assigned assessment schedule and ascertain if the subject wishes to and / or should continue in the study.
- Before a subject is deemed lost to follow-up, the Investigator or designee will make every effort to regain contact with the subject (at minimum 3 telephone calls and a certified letter to the subject's last known mailing address or local equivalent methods). These contact attempts must be documented in the subject's medical record or study file.
- Should the subject continue to be unreachable, he or she will be considered lost to follow-up from the study.

All applicable eCRFs up to the point of subject withdrawal / lost to follow up and an "End of Study" eCRF must be completed.

6.6 *Subject Status and Classification*

As subjects are evaluated, enrolled, and treated in the study, they will be grouped into one of the following categories. Categorization will determine follow-up, data, and analysis requirements.

Investigational sites will list all Consent Ineligible (screening failure), Intent, Attempt and Treatment subjects in the Screening and Enrollment Log.

6.6.1 **Consent Ineligible (Screening Failures)**

A subject who has signed informed consent but is found ultimately not to meet eligibility criteria will be classified as "Consent Ineligible".⁶ There are no follow-up reporting requirements for consent ineligible subjects. Subjects determined to be Consent Ineligible do not count towards the enrollment ceiling and will not be used for analysis of the endpoints. The original signed Informed Consent must be maintained in the center's patient file. A subject ID will be assigned in the EDC system.

For consent ineligible subjects the following forms must be completed:

- Enrollment and End of Study eCRF must be completed
- Adverse Event CRFs for any reportable event, as defined in **Section 17** for any adverse event that occurs after signing the Informed Consent, up to the point of subject withdrawal

6.6.2 **Roll-In Subjects**

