8.1.1.3 Statistical Methods

The proportion of Treatment Subjects and Attempt Subjects with one or more CSAEs will be estimated using the Kaplan-Meier method. The 97.5% one-sided upper confidence limit of the observed event rate will be compared to the performance goal of 12%. If the upper confidence limit is less than the performance goal, the null hypothesis will be rejected. The upper confidence limit will be calculated as the pointwise confidence limit using the log-log methodology.

Subjects who withdraw from the study prior to the Assessment Day (Day 360 Assessment for Treatment, Day 30 Assessment for Attempt) without experiencing a primary endpoint event will be censored on the date of withdrawal. Subjects who undergo a second re-ablation procedure or a re-ablation procedure following the Blanking Period without experiencing a primary endpoint event will be censored as of the date of that re-ablation procedure. Subjects who are determined to be Severe COVID-19 Subjects during trial participation without experiencing a primary endpoint event will be censored as of the Onset Date of the condition.

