The table below shows the meta-analysis results, with expected rate 67.23% [62.87%, 71.46%] from the random effect model. There are differences in methods when comparing these trials: these include different AAD management after blanking period (patients off AAD or under stable dose of previous AAD) or different methods for monitoring of recurrences (Holter monitoring frequency and duration, frequency of reporting from EMs). A selection of studies with a strictly uniform set of methods would lead to too few data to analyze in the meta-analysis. Accordingly, a conservative approach has been applied and a value of 55% has been selected for the expected rate of the PEE, to acknowledge the methods differences and multiple variance sources. This is justified by the following aspects: (1) Acute Procedural Success is considered both as successful isolation of the PV and the LAPW and all studies analyzed do not consider LAPW isolation success as part of the endpoint (2) the FARAPULSE PFA System is different from those of listed studies in which either Cryoballoon ablation or RF ablation or other ablation systems were utilized.

Table 8.1-3: Meta-Analysis to Determine Primary Effectiveness Endpoint Parameters

Study	Design Info.	Ablation Technology	Event /Total	Rate (%)	95% CI
PRECEPT Trial	IIDE, Prospective, multicenter, PersAF	RF with THERMOCOOL SMARTTOUCH SF catheter (PVI)	234/333	70.27	(65.05, 75.13)
Schmidt et al., 2017	Randomized, multicenter, drug-refractory PersAF	Laser Balloon vs. RF (PVI WACA)	96/134	71.64	(63.21, 79.09)
Adiyaman et al., 2018	Prospective, randomized, early PersAF	RF vs. Surgical	14/26	53.85	(33.37, 73.41)
Chauhan et al., 2021 (pvi)	Randomized, single-center, high-burden PAF or PersAF	CFS catheter Smart-Touch SF (PVI)	20/40	50.00	(33.80, 66.20)
Chauhan et al., 2021 (pvi+)	Randomized, single-center, high-burden PAF or PersAF	CFS catheter Smart-Touch SF (PVI + FaST mapping/ablation)	28/38	73.68	(56.90, 86.60)
Mortsell 2019	Prospective, randomized, PersAF	Arctic Front Advance (Cryo)	51/62	82.26	(70.47, 90.80)
Wynn et al., 2016	Prospective, multicenter, randomized, PersAF + sustained PAF	PVI vs. PVI + lines	81/122	66.39	(57.28, 74.69)
Dong 2015	Prospective, randomized, single center, PersAF	RF (PVI +)	93/146	63.70	(55.34, 71.49)
REAFFIRM Trial	Randomized, PersAF	RF (PVI vs. PVI+ FIRM)	239/350	68.29	(63.13, 73.13)
STOP Persistent AF Trial	IIDE Prospective, PersAF	Cryo (PVI)	114/186	61.29	(53.89, 68.33)

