<small>*PersAF - Persistent AF, PAF - Paroxysmal AF, CFS - Contact Force-Sensing, PVI - Pulmonary Vein Isolation</small>					
Overall				67.23	(62.87, 71.46)
<small>* Overall Rate, 95% CI calculated using a binary random effects model</small>					

A PEE performance goal of 40% has been chosen based on the minimum chronic acceptable success rate for PersAF at 12-month follow-up defined in the 2017 HRS / EHRA / ECAS Expert Consensus document.⁸ The recommendation for evaluating the effectiveness of a treatment for PersAF described as:

“If minimum chronic success rate is selected as an objective effectiveness endpoint for a clinical trial, we recommend that the minimum chronic acceptable success rate for PersAF at 12-month follow-up is 40%.”

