8.1.2.2 Sample Size

The sample size estimate was obtained using the binomial exact method. The following assumptions were used in the sample size calculation:

Table 8.1-4: Assumptions for the Primary Effectiveness Endpoint Sample Size Estimate

Assumptions	Primary Effectiveness Endpoint
Expected rate	55%
Performance goal	40%
Attrition (per year)	10%
Significance level (one-sided)	0.025
Power	90%
Evaluable subjects	122
Subjects accounting for attrition	136

Under the methods and assumptions outlined above, the required sample size for this endpoint after attrition is 122, therefore a minimum of 136 Treatment Subjects are required for the analysis of primary effectiveness endpoint.

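### For the primary effectiveness endpoint, mainly in Phase 1, censoring at the withdrawal date can credit silently lost subjects with event-free time that nobody observed

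*Combined protocol and SAP*

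**What the plan says.** Section 8.1.2.3 (Phase 1) estimates Treatment Success through the Day 360 Assessment by Kaplan-Meier and compares a one-sided 97.5% log-log lower limit with the 40% performance goal. Subjects who withdraw or die before that assessment without an endpoint event "will be censored on the date of withdrawal or death". Appendix A Section 8.1.2.3 has the same rule. The safety paragraph in Section 8.1.1.3 is parallel: subjects who withdraw "without experiencing a primary endpoint event will be censored on the date of withdrawal".

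Section 6.4 makes loss to follow-up a kind of withdrawal: "Reasons for withdrawal may include physician discretion, subject choice to withdraw, lost to follow-up, or death". Section 6.5 says when that status is given. The subject must first miss a scheduled assessment, and then "Before a subject is deemed lost to follow-up, the Investigator or designee will make every effort to regain contact with the subject", which means at least three telephone calls and a certified letter.

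Section 7.1 sets the Day 180 Assessment at 180 ± 30 days and the Day 360 Assessment at 360 ± 30 days, with no scheduled visit between them. Section 23.2 defines the Exit Date as the day participation ends. Nothing in the protocol or its appendices ties the censoring date of a lost subject to the last contact, visit or rhythm recording.

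**The concern.** Kaplan-Meier is valid here only if a subject leaves the risk set when ascertainment stops. For an active withdrawal or a death, the date is known and the rule works. For a subject who simply stops responding, the withdrawal date is naturally the date on which loss is declared, and that date trails the last information by months. Someone last seen shortly after Day 180 is missed at a visit whose window runs from Day 330 to Day 390.

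In the interval the subject stays in the risk set and cannot fail, because re-ablation, cardioversion, drug use and (in Phase 1) rhythm are no longer being reported. This raises the success estimate. In a single-arm study whose only effectiveness test is against a fixed goal, it also makes a false pass more likely when the true rate is at the goal. Phase 1 lists no missing-data sensitivity analysis that would reveal it.

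**Working it through.** **The plan's own figure.** The expected rate is given by "a value of 55% has been selected for the expected rate of the PEE" and the null by "A PEE performance goal of 40% has been chosen" (both Section 8.1.2). By exact binomial with n = 122, the rule is to pass with at least 60 successes:

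- P(X ≥ 60 | 122, 0.40) = 0.0248
- P(X ≥ 60 | 122, 0.55) = 0.916, against the stated 90%
- 122 / (1 − 0.10) = 135.6, so 136

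The figures in Table 8.1-4 reproduce. The analysis itself uses all Treatment Subjects (Section 8.2.1), planned at 258, so N = 258 below.

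**Assumptions that are not in the documents.** Silent loss is exponential, 5% or 10% by Day 360, and independent of outcome. True success is 40% at Day 360, with a constant failure hazard from Day 90: λ = −ln(0.40)/270 = 0.00339 per day. The curve is read at Day 360. A lost subject is censored when the next missed window closes: Day 104 if lost before Day 90, Day 210 if lost on Days 90–180, Day 390 if lost later.

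**How many subjects (10% loss).** The fraction lost between Day 180 and Day 360 is 0.9^0.5 − 0.9 = 0.0487, and 0.0487 × 258 = 12.6. With S(180) = 0.737 and S(360) = 0.400, mean event-free probability over the interval is (0.737 − 0.400)/(0.00339 × 180), about 0.551. So 12.6 × 0.551, about 6.9, are event-free when lost.

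**Bias by hand, first order (10% loss).** Each item is the number of failures that go unseen, converted to points at Day 360.

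- Lost on Days 180–360: 12.6 × (0.551 − 0.400) = 1.9 unseen failures, and 1.9/258 = 0.74 points.
- Lost on Days 90–180: 6.5 subjects, mean S = 0.862, S(210) = 0.665. Unseen: 6.5 × (0.862 − 0.665) = 1.28. Effect: (1.28/258) × (0.400/0.665) = 0.30 points.
- Lost before Day 90: 6.7 × (1 − 0.954) = 0.31. Effect: (0.31/258) × (0.400/0.954) = 0.05 points.

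The total is 0.74 + 0.30 + 0.05 = 1.09 points. At 5% loss it is about half that.

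**Simulation of the planned test** (Kaplan-Meier, log-log lower limit against 40%, 8,000 to 10,000 trials per setting, true rate 40%, N = 258):

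| Yearly silent loss | Censoring date | Mean estimate | Type I error |
|---|---|---|---|
| 5% | last contact | 40.0% | 0.022 |
| 5% | close of next missed window | 40.5% | 0.033–0.036 |
| 10% | last contact | 40.0% | 0.022 |
| 10% | close of next missed window | 41.1% | 0.049 |

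At 10% loss I varied the late censoring day (345, 375 or 395), the read-off day (360 or 390) and the share of the hazard before Day 180 (one third or 60%). Type I error stayed between 0.040 and 0.054, and the mean estimate between 40.9% and 41.2%.

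**At the expected rate.** With a true 55% and 10% loss, the mean estimate moves from 55.0% to 56.0%. Power is 99.7% with last-contact censoring and 99.9% with late censoring.

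**The case against.** The strongest reply is that the plan does not say how a loss to follow-up is dated. Sections 6.4 and 6.5 also name withdrawal and loss side by side, the Exit Date could be taken as last contact, and the read-off day is not stated. Parts of the analysis are deferred to a SAP whose text is not in these documents. This stands in part: late dating is the natural reading, not the only one, and a last-contact rule elsewhere would cure it. A reader might infer that every subject lost after Day 180 is necessarily carried past Day 360. The documents do not support that, because the window opens at Day 330 and loss could be declared earlier. The bias is nearly the same at Day 345, however.

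A reader might also infer a type I error of 0.10 to 0.15. That figure arises only if the whole 10% attrition is silent loss and every such subject is dated after Day 360. Section 6.4 attrition includes deaths and active withdrawals, whose dates are known. A subject lost before Day 180 is missed at the Day 180 visit, whose window closes at Day 210. With last contact uniform over Days 90–360, dating those early losses at Day 210 brings the 10% case from 0.094 down to 0.054.

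A third tempting inference is that the safety tests are inflated too. After the 30-day window only PV stenosis and atrio-esophageal fistula count (Tables 3.2-1 and 3.3-1), and Appendix A Section 8.1.1 says all events in its meta-analysis began within 30 days. Little event risk remains in the uncovered time, and no inflation has been demonstrated.

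Finally, information continues between visits. Phase 1 asks for two event-monitor transmissions a month with compliance follow-up (Section 11.1.1), but silence there is not the trigger for loss to follow-up and sets no censoring date. In Phase 2 the LUX-Dx may go on transmitting, sites should contact subjects disconnected for more than 7 days, and a tipping-point analysis is planned (Appendix A Sections 7.6 and 8.3.3.1). These partly mitigate the problem without changing the primary test.

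**Conclusion.** The point holds for the primary effectiveness endpoint, chiefly in Phase 1. Read naturally, the censoring rule credits silently lost subjects with unobserved event-free time. At 5% to 10% yearly silent loss the estimate is about 0.6 to 1.1 points too high when the true rate is 40%, and the one-sided type I error is about 0.035 to 0.05 rather than 0.025. The 10% end treats all the planned attrition as silent loss, so it is towards the upper side.

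The figures rest on loss unrelated to outcome, a constant hazard after blanking, and dating at or near the next missed visit. If recurrence made loss more or less likely, the size would differ, and the documents give nothing to estimate that. At the planned 55% the pass or fail result would hardly ever change. What suffers is error control near the goal and the accuracy of the reported rate. This should be corrected, but it does not threaten the design.

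**What to change.** In both effectiveness censoring paragraphs (Section 8.1.2.3 and Appendix A Section 8.1.2.3) and in the SAP, state that event-free subjects who withdraw or are lost are censored at the last date on which endpoint status was ascertained. That is the last completed assessment, contact or evaluable study rhythm recording, including LUX-Dx transmissions in Phase 2. Add that the date of declaring loss to follow-up, or of the end-of-study form, is never used. Align the safety paragraphs (Section 8.1.1.3 and Appendix A Section 8.1.1.3) for consistency.

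The cost is one sentence in each place. Visit, contact and transmission dates already exist, so no new data are needed. Precision falls slightly and the estimate becomes slightly less favourable. At 10% loss and a true 55%, power with 258 subjects is still about 99.7%.

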8.1.3 Other Endpoints and Assessments

The following analyses will also be performed as defined in the referenced sections using descriptive statistics:

- Additional Safety Endpoints (**Section 3.4.1**)
- Additional Effectiveness Endpoints (**Section 3.4.2**)
- Procedural Assessments (**Section 3.4.3**)
- Quality of Life Assessments (**Section 3.4.4**)

8.2 General Statistical Methods

8.2.1 Analysis Sets

While each primary endpoint was individually powered, each endpoint analysis will use all available data: Attempt and Treatment Subjects will be used for persistent AF safety endpoint analyses unless otherwise clarified, and Treatment Subjects will be used for persistent AF effectiveness endpoint analyses.

Roll-In Subjects: Endpoint data will be summarized separately. Roll-In subjects will not be used in the main primary endpoint analyses.

8.2.2 Control of Systematic Error / Bias

Control and reduction of potential bias associated with a single-arm study design have been addressed by a series of measures including but not limited to:

- Patients meeting the eligibility criteria and signing the ICF will be eligible for sequential enrollment in the study.
- ECG, Holter monitoring, and event monitoring data will be evaluated by a third-party Arrhythmia Core Laboratory according to standardized protocols.
- Cardiac MRI / CT images utilized for assessing potential PV stenosis will be evaluated by a third-party Cardiac Imaging Core Laboratory according to standardized protocols.
- The use of a comprehensive set of study procedures as defined in the protocol which ensure consistent patient management.
- Comprehensive site and data monitoring to ensure accurate and complete recording of study data.
- The use of an independent Clinical Events Committee (**Section 19.2**) will review and adjudicate all potential SAEs and primary safety outcomes.
- Creation of a complete Clinical Study Report and full dataset to allow scientific and clinical reviewers to independently assess potential error and bias.

To avoid any center effect and bias, no center will be authorized to enroll more than 33 Treatment Subjects (13% of the total planned enrollment of 258 Treatment Subjects).

8.2.3 Study Success and Control of Type I Error

Both the primary endpoints must pass in order to achieve study success. Each primary endpoint will be tested at a significance level of 2.5% while still maintaining the overall Type I error level at no greater than 2.5%. This follows the methodology of the Intersection-Union Test (IUT).

8.3 Data Analyses

8.3.1 Roll-In Subject Analyses

The stipulated analyses for Roll-In Subjects will be summarized with descriptive statistics. Endpoint data for Roll-In Subjects will be summarized but no hypothesis testing will be performed.

8.3.2 Interim Analyses

No formal interim analyses are planned for the purpose of stopping the study early for declaring success or futility. Analysis of each endpoint will be performed for regulatory submission when all applicable data for that endpoint has been collected,⁹ dependent on specific geographic requirements where applicable. The ADVANTAGE AF Study may be used to satisfy the requirements of multiple regulatory bodies. Details on these analyses will be included in the ADVANTAGE AF SAP when available.

8.3.3 Subgroup Analyses

An analysis will be performed to evaluate whether any significantly different effects exist in the primary endpoints within subgroups of subjects. The list of covariates (with applicable subgroups in parentheses) will include at least the following:

⁹ Additional data analysis and reporting may be performed after a sub-set of subjects have completed their Assessment for regulatory submission outside of the United States.

- Subject demographics (e.g., age-[e.g. age >=65 vs. <65, Medicare eligible], gender)
- Subject baseline characteristics (e.g., LVEF, cardioversion history, BMI, and LA diameter)
- Index Procedure lesion sets
 - PV + LAPW ablation alone versus PV + LAPW plus additional ablations
 - CTI ablation versus no CTI ablation
- Geography
- FARAPULSE PFA System used (Investigational vs. Commercial)

Each subgroup covariate will be included as a single independent variable in a logistic regression model with the primary endpoint outcome as the dependent variable and a test for significance at the 15% level will be performed.

In addition to subgroup analyses, descriptive statistics of subject demographic and baseline characteristics will be presented for each subgroup listed in this section.

